Study Title	Expanding use of continuous glucose monitoring beyond COVID in critical care: Impact on nurse work patterns and patient outcomes
NCT Number	N/A
Document Description	Study Protocol and Statistical Analysis Plan
Date	April 26, 2022

Research Protocol

Expanding use of continuous glucose monitoring beyond COVID in critical care: Impact on nurse work patterns and patient outcomes

I. Objectives

The **primary objective** of this mixed methods hybrid II implementation study is to assess the feasibility of real time continuous glucose monitoring (CGM) implementation using a CGM plus (+) point-of-care (POC) protocol among patients on IV insulin or those with hyperglycemia ($>250\text{mg/dl}$) in the critical care hospital environments. Use of the hybrid II implementation study design will allow simultaneous evaluation of implementation and effectiveness outcomes to promote more rapid adoption of CGM as routine care for hospitalized patients.

The research Questions (RQ) we hope to address in this study are:

RQ 1: Establish the clinical utility, fidelity, and adoption of Dexcom G6 CGM as a tool for making dosing decisions within a CGM+POC protocol among medical intensive care unit (MICU) patients. We will conduct a prospective observational cohort study among MICU patients using Dexcom G6 CGM therapy (N=100). *Clinical utility criteria:* Time to CGM validation within protocol parameters, mean percent of dosing decisions determined by CGM, changes in insulin dosing from standard guideline or outside standard times in response to alarm and/or trend data (as measured by manufacturer download data and corresponding electronic health record (EHR) documentation). *Fidelity criteria:* Proportion of times CGM used non-adjunctively/number of times non-adjunctive use indicated per protocol. *Adoption criteria:* Proportion of patients who consent to received initial CGM monitoring/number of patients eligible to receive initial CGM monitoring. **Hypothesis:** The majority of insulin dosing decisions will be made using non-adjunctive CGM and CGM will alter nursing dosing decisions from standard guidelines.

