A CGM + POC protocol was developed and implemented within OSUWMC MICU unit. The protocol, which allows for intermittent non-adjunctive CGM use with requisite initial validation within each patient and continued validation Q6 hours, proved successful in facilitating safe and effective CGM implementation in over 132 critically ill patients with COVID-19. The CGM + POC protocol require comparison of paired sensor-meter readings. The comparison standard method (Novo StatStrip POC meter) and source (capillary, arterial, venous) are FDA approved for inpatient use. In an effort to mitigate risk in this study among critically ill MICU patients, we propose a more conservative strategy with increased frequency of ongoing POC testing and validation every 4 hours. Additionally, more frequent testing at Q2 or Q1 hours will occur during periods of clinical change that could proceed a decline in CGM accuracy. The standard is compared to the CGM value obtained within 5 minutes. The threshold criterion for nonadjunctive (stand-alone) use of the CGM to inform insulin dosing decisions appears in Table 1. CGM values will be used to determine insulin doses within standard OSUWMC guidelines (e.g., IV infusion guideline) and provider prescribed orders. Alert thresholds are set at 100 mg/dl (lower threshold) and 300

mg/dl (upper threshold). In addition, the Urgent Low Soon alert will be activated and designed to provide a 20-minute advance warning of impending hypoglycemia, so nurses can act quickly to avoid a potential severe hypoglycemic event.

Table 1. Initial and Ongoing CGM Validation

Stage	POC glucose testing procedures
CGM validation	
POC glucose testing Q1 hour compared to CGM glucose
 
Proceed to Q4 hour POC testing when two consecutive sensor-meter pairs approximately 1-hour apart meet either of the following criteria:
 
 1) CGM <20% difference from the POC when the glucose is >100 mg/dl 2) CGM <20 mg/dl difference from the POC when the glucose is <100 mg/dl

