Nurse training: OSUWMC MICU nurses have significant experience with CGM use in an extremely ill cohort of COVID-19 patients. Each nurse in the MICU receives training on CGM set-up, insertion, pairing, and CGM glucose monitoring features as part of their annual critical care competencies. OSUWMC MICU nurses are trained and experienced in using POC glucose measurement to validate the CGM system, however the protocol at use in this study differs somewhat from the COVID-19 protocol currently at use in the MICU. Given that, nurses will receive training on distinctions between the two protocols including changes to the frequency of POC testing, the addition of clinical status events that would warrant more frequent POC testing and validation (Q1 or Q2 hours depending on number of events present for a duration of 6 hours). New criteria to stop clinical use (i.e., no use of CGM for glucose monitoring, no use of CGM for insulin titration) will be reviewed in detail with nursing along with plans for the sensor to remain in place only for data collection. Nursing trainings will be conducted by PI ([name]), Co-I ([name]), and study coordinator during staff meetings and nursing huddles conducted on all shifts. All nurses will receive training on the new protocol prior to patient recruitment. The study protocol, along with currently available training materials, will be kept at the bedside of all patient participants.

Staggered enrollment and initial pilot: We will stagger enrollment with just 20 patient participants over a 4-week period (target 5 participants/week with a respite between enrollment to allow analysis of safety and fidelity data prior to the next round. A robust analysis would be conducted after this first “pilot” round of enrollment. Accuracy analysis would include MARD and Clark Error Grid. A full assessment of protocol adherence and evaluate adherence to standard insulin dosing guidelines will be completed. The pilot analysis will include evaluation of

benchmarks for accuracy, safety, and adverse event monitoring with benchmarks that must be met prior to subsequent enrollment. Pilot benchmarks for study continuation are as follows:

- Successful initial validation criteria within 24 hours in 80% of participants (16/20)
- Clark error grid analysis demonstrating >95% points in zone A (within 20% of reference glucose value) or zone B (outside of 20% but would not lead to inappropriate treatment) following initial validation.

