- No more than 1 episode of inappropriate insulin dose resulting in severe hypoglycemia (glucose <55mg/dl) after initial sensor validation
- No more than 1 episodes of iatrogenic DKA (pH <7.3 or serum bicarbonate <15 mEq/L in the setting of elevated ketones) or hyperosmolar nonketotic state (osmolality \geq 320mOsm/kg with BG >600mg/dl and pH >7.3 or serum bicarbonate >15 mEq/L)
- No episodes of severe adverse events resulting in prolonged hospitalization, or other life-threatening complication that attributed to the study intervention
- No severe adverse events resulting in death, or other life-threatening complication that is attributed to the study intervention
- No severe adverse event resulting in prolonged hospitalization, or other life-threatening complication that attributed to the study intervention and is expected to recur

Oversight and monitoring. Study team oversight of nursing use of the CGM system will be performed through a combination of (1) daily evaluation of EHR and CGM Clarity data and (2) through rounding on CGM patients (mon-Friday by PI ([name]), Co-I ([name]) and/or study coordinator (to be named) (Saturday, Sunday and holidays by the MICU charge nurse who will communicate that day with study team members. Daily rounds will allow the study team to continuously evaluate protocol fidelity and identify any safety concerns. The study staff will evaluate CGM use daily through Clarity CGM and EHR data to determine the following:

3. Was initial validation criteria achieved correctly and at what frequency
4. Is ongoing validations performed Q4 hours and according to validation criteria
5. If validation is met did the nurse begin hybrid use with non-adjunctive CGM use
6. Using clarity reports study staff will assess the presence of alarms (e.g., <100mg/dl, >300mg/dl, predictive hypoglycemia) Alarms will be reviewed daily by research staff to ensure hypoglycemia and hyperglycemia are being treated in accordance with OSUWMC guidelines.
7. Those patterns of hyperglycemia or hypoglycemia assessed every 24 hours, will be reported to primary team via pager/direct message to allow changes to insulin dosing as needed (e.g., max drip rate for IV insulin titration).
8. Assessment of change in clinical status criteria (Table 1) in which per protocol the nurse would increase frequency of POC testing and validation.

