9. Assessment of Stop CGM use criteria (Table 1) in which per protocol the nurse would no longer use the CGM for glucose monitoring or insulin titration.

RQ 1: Establish the clinical utility, fidelity, and adoption of Dexcom G6 CGM as a tool for making dosing decisions within a CGM+POC protocol among medical intensive care unit (MICU) patients.

Rationale/Approach. We will conduct a prospective cohort observational analysis among critically ill patients on IV insulin or those with hyperglycemia (>250mg/dl) in OSUWMC MICU. The research will allow us to examine the clinical utility and implementation of CGM as the standard of care in a critical care environment. We hypothesize that the majority of insulin dosing decisions will be made using non-adjunctive CGM and CGM, with the availability of trend and alarm data, will alter nursing dosing decisions from standard guidelines.

Procedures. Once consent is obtained, the MICU staff nurse will insert the Dexcom G6 sensor, set up the system, pair the transmitter on patients, and connect patient data to a centralized nurse's station CGM Dashboard in the MICU (N=100). The CGM + POC protocol will be used to validate at which time the CGM will be used for non-adjunctive insulin dosing decisions. POC testing will be performed Q4 hours for continued validation of the CGM with more frequent sustained POC validation during periods of rapid clinical change (Table 1).

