The Android phone, which will receive glucose data from the CGM transmitter, will be kept outside of the patient room allowing the staff nurse to visualize discrete values, trends and hear alarms without entering the patient's room. OSUWMC MICU employs a staffing ratio maximum of 1 nurse for 2 patients. MICU staff nurses will only care for 1 patient using CGM at a time. Alarms are visually displayed and audible from both the dashboard and receiver (Android phone); however nurses are instructed to confirm all glucose values and the presence of alarms on the receiver devices at the bedside prior to treatment. All nurses in the MICU are trained on CGM alarm recognition and response. In a previous analysis, nurses reported alarms were audible throughout the MICU unit.² If the nurse assigned to the CGM patient participant is not immediately available when an alarm is sounding, another nurse or the charge nurse is expected to respond to the alarm and provide appropriate treatment. This same alarm response delegation is employed for other MICU systems including cardiac telemetry, Pulse oximetry, and ventilator alerts. Nurses will follow standard approved OSUWMC guidelines, policies and provider dosing orders for treatment of hyperglycemia and hypoglycemic events. Episodes of hypoglycemia and hyperglycemia will be responded to in real time by nursing staff. Our hypoglycemia guideline (Table 3) treats glucose <80mg/dl with Dextrose D50% for critically ill patients. Dosing is stratified based on degree of hypoglycemia with follow-up required within 15 minutes. For hypoglycemia <60mg/dl nurses are instructed to inform the provider via pager/direct chat. Nurses in the MICU are experienced in administration dextrose D50% using the described hypoglycemia protocol. If the patient is ordered to undergo magnetic resonance imaging (MRI), computerized tomography (CT) radiographic procedures, or diathermy than the sensor/transmitter will be removed prior to the procedure as these procedures could potentially interfere with sensor accuracy.²⁹ A new sensor will be inserted after procedure is completed and will undergo initial validation prior to use.

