The patient will remain on CGM for the duration of their hospital stay and if discharged to home may transition to personal use of the Dexcom G6. The Dexcom G6 sensor is replaced every 10 days and will be removed and then replaced for some radiographic procedures or sensor failure. CGM data is automatically transferred to Dexcom's cloud-based Clarity system.

Table 3. OSUWMC Hypoglycemia Guideline, Patients Who are Not Alert, Are NPO, or on IV Insulin Infusion

Blood Glucose (BG) Level*	Action	Follow-Up
60-79 mg/dL	
 • Administer 7.5 g Dextrose D50% (15 ml) IV* • Consider calling House Officer if patient experiencing recurrent BG <70 mg/dL in past 12 h 	
 • Recheck BG q 15 min following treatment and treat accordingly until ≥ 80mg/dl • Once ≥ 80mg/dl, recheck BG q1h x2 (x4 if <45mg/dL at onset), then resume POC glucose as previously ordered, Patients who are admitted with hypoglycemia should be monitored at least q 4h for a minimum of 24h
45-59 mg/dL	
 • Administer 12.5 g Dextrose D50% (15 ml) IV* • Call House Officer to report BG and action taken 	
<45 mg/dL	
 • Administer 25 g Dextrose D50% (15 ml) IV* • Call House Officer to report BG and action taken 	
ALL	
 • Consider adding Dextrose 5% to maintenance IV fluids at a rate of ≥ 50ml/hr or increase rate of existing maintenance IV if dextrose source already present 	
 • If > 4h from initial event and BG ≥ 80mg/dl for two consecutive readings, may consider reducing IV dextrose

Variables and measures. *Clinical utility criteria:* Time to CGM validation within hybrid protocol parameters, mean percent of dosing decisions determined by CGM, changes in insulin dosing from standard guideline or outside standard times in response to alarm and/or trend data (as measured by manufacturer download data and corresponding EHR documentation). *Fidelity criteria:* Proportion of times CGM used non-adjunctively/number of

times non-adjunctive use indicated per protocol. *Adoption criteria:* Proportion of patients approached to received CGM monitoring/number of patients eligible to receive initial CGM monitoring.

RQ 2: To assess the degree to which CGM implementation within the ICU environment effects nursing workload and care delivery.

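### RQ1 counts a nurse-initiated, alarm- or trend-prompted departure from the insulin guideline as clinical utility, while the protocol elsewhere requires and checks adherence to that guideline

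*Combined protocol and SAP*

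**What the plan says.** The statements on one side are in RQ 1:

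- Section I, RQ 1, and again RQ 1 Variables and measures in III.C, list as clinical utility "changes in insulin dosing from standard guideline or outside standard times in response to alarm and/or trend data". The patient schedule of activities (Table 2, Aim 1) has the same item, collected daily from the EHR and the Clarity download.
- The hypothesis in Section I is that "CGM will alter nursing dosing decisions from standard guidelines". The RQ 1 Rationale in III.C repeats it and gives the mechanism: CGM, "with the availability of trend and alarm data, will alter nursing dosing decisions from standard guidelines".

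The statements on the other side are in the procedures:

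- Section II, CGM + POC Protocol: "CGM values will be used to determine insulin doses within standard OSUWMC guidelines (e.g., IV infusion guideline) and provider prescribed orders".
- III.C, RQ 1 Procedures: "Nurses will follow standard approved OSUWMC guidelines, policies and provider dosing orders for treatment of hyperglycemia and hypoglycemic events".
- III.C, Staggered enrollment and initial pilot: "A full assessment of protocol adherence and evaluate adherence to standard insulin dosing guidelines will be completed".
- III.C, Oversight and monitoring, item 6: "Alarms will be reviewed daily by research staff to ensure hypoglycemia and hyperglycemia are being treated in accordance with OSUWMC guidelines".

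Item 7 of the same oversight list adds a further route to a dose change. Patterns of high or low glucose, assessed every 24 hours, "will be reported to primary team via pager/direct message to allow changes to insulin dosing as needed".

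For RQ1, III.D Data Analysis names multivariate linear models with patient-condition covariates and says nothing on how a dosing change is classified.

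**The concern.** Under the hypothesis, more alarm- or trend-prompted departures from the guideline mean more support for CGM. Under the dosing rule and the adherence checks, the same departures are something the study team looks for as a fault. A reader given only the pooled RQ1 figure cannot tell how much of it is timely action within the rules and how much is dosing outside them.

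The criterion also takes no account of what follows. A departure that ends in glucose below 55 mg/dl adds to utility exactly as one that prevents hypoglycemia does. If the classification is left open, it may be settled after the data are seen.

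Attribution is a second, smaller matter. The stated sources are Clarity and the EHR. These may not distinguish a nurse's own response to an alarm or trend from a dose change made after the study team messaged the primary team. That message would be absent in routine use.

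**Working it through.** The plan states no figure for this criterion. Its only sample-size calculation concerns time in range and does not bear on the point. The check is therefore to take each kind of dosing change and ask how each part of the document treats it.

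| Dosing change | RQ1 utility criterion | Dosing rule and adherence checks |
|---|---|---|
| A. Prompted by alarm or trend, outside standard times, dose agrees with guideline | Counts | Cannot be judged; the insulin guideline is not reproduced |
| B. Prompted by alarm or trend, dose differs from guideline, provider order covers it | Counts, as worded | May comply, since the CGM + POC Protocol allows for provider orders |
| C. Prompted by alarm or trend, dose differs from guideline, nurse-initiated, no order covers it | Counts | Non-adherent |
| D. Dose differs from guideline, no alarm or trend involved, no order covers it | Does not count | Non-adherent |
| E. Changed after a study-team message to the primary team | Not stated | May comply, if made under an order |

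Row C is the conflict: one event, two opposite readings, and no text that chooses between them. The word non-adherent is this review's; the documents require and assess adherence but give such an event no label.

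Size. Leave row E aside and write a, b and c for the counts in rows A, B and C. The pooled measure is

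U = a + b + c.

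The conflicting share is c / U. The documents give no number of dosing decisions, no departure rate and no split between the rows, so the share is bounded only by:

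- c = 0, which gives c / U = 0;
- a = b = 0, which gives c / U = U / U = 1.

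Any value of U is compatible with any share from 0 to 100%. Adjusting U for SOFA score, renal replacement, ventilator support and pH, as III.D plans, does not change this, because a covariate model for the total does not identify its parts.

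Outcome. The pilot benchmark (no more than 1 episode) and the stopping criterion in IV.E (at least 2 episodes) both concern an inappropriate insulin dose followed by glucose below 55 mg/dl. Neither defines inappropriate. A row C event with that result could therefore support RQ1 and also count toward stopping.

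**The case against.** The strongest reply is that this is only a missing definition, and that the plan has other protections. RQ1 is an observational cohort with no success threshold for this measure. Harm is tracked elsewhere: time below 70 and below 55 mg/dl is analysed daily, and inappropriate doses leading to glucose below 55 mg/dl are both a pilot benchmark and a stopping criterion. Guideline adherence is assessed in the pilot but is not among the listed continuation benchmarks and has no threshold, so no stated decision hangs on the double reading. The RQ1 fidelity ratio covers only non-adjunctive use, so there is no conflict within it.

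All of that is correct, and it limits the point to interpretation. It does not remove it, because none of those safety measures is linked to individual departures and no text says how row C is classified.

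A reader might go further and infer four things that the documents do not support:

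- That full compliance makes this part of the hypothesis fail by design. The insulin guideline is not reproduced and may allow nurse judgement. Changes under an order may comply, and the criterion also counts dosing outside standard times.
- That poor compliance makes it succeed. Only changes prompted by an alarm or trend count; row D lowers adherence and adds nothing to utility.
- That each departure moves utility and adherence by equal and opposite amounts. Neither quantity has a stated denominator, and the trigger differs.
- That study-team messages inflate the result. They go to the primary team, the hypothesis concerns nurses, and no text says that such changes will be credited to nursing use of CGM. It is a possibility to be excluded.

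**Conclusion.** The point holds as a contradiction between the RQ1 criterion and hypothesis on one side, and the dosing rule and adherence checks on the other. It is confined to nurse-initiated departures that are prompted by an alarm or trend and not covered by a provider order. For those events the plan's text supports both utility and non-adherence, regardless of outcome.

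Its size is unknown: from none to all of the pooled measure. The consequence is that the measure, reported as planned, cannot show whether CGM prompted useful dosing action. The conclusion rests on the text alone and assumes that no unreproduced guideline or order set already classifies these departures. It does not invalidate the other RQ1 measures, and it should be settled before analysis.

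**What to change.** 1. Reconcile the RQ 1 hypothesis and criterion (Section I; III.C, RQ 1) with the CGM + POC Protocol, the RQ 1 Procedures, the pilot analysis and the oversight list on how a CGM-prompted departure is classified. Which dosing rule applies is for the authors; this review takes no position.

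2. Report the two limbs separately:
   - (a) alarm- or trend-prompted actions outside standard times where the dose agrees with the guideline or an order;
   - (b) doses that differ from the guideline, split by whether a provider order covered them, shown beside the adherence results with subsequent glucose below 70 and below 55 mg/dl.

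   Do not read (b) alone as evidence of utility. An action outside standard times that follows an order but differs from the guideline fits both limbs, so state in advance where it is counted.

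3. Log each study-team message sent under Oversight and monitoring, item 7, and report dose changes that follow one separately.

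The cost is protocol and analysis wording, some analysis work on EHR and Clarity data already collected, and one small new log field, since the documents do not say that messages are logged. The reported utility figure may be smaller.
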